Among the healthy controls, 19/19 (100%) were able to generate PIFR >120 L/min when no internal resistance was applied. PIFR was 97 ± 13 L/min with Diskus® resistance and 55 ± 7 L/min with Handihaler® resistance. Overall, 15 (55%) of COPD patients were not able to generate optimal PIFR (defined as >45L/min for this study) on at least one prescribed DPI. Compared to COPD patients able to generate optimal PIFR, discordant COPD participants had a greater prevalence of uncontrolled COPD (defined as COPD Assessment Test \geq 10): 93% versus 83%. Among nine

participants with repeated measures over two weeks, there were no statistical differences between intersession measurements for any inhaler resistance setting. These preliminary data demonstrate that suboptimal PIFR is common in stable COPD and may correlate with symptom burden.

Preliminary data has also demonstrated stability in PIFR over 2-4 weeks, suggesting this is inadequate duration to capture full spectrum of variability. Specifically, preliminary data from 15 COPD participants who underwent repeated measures at two to four weeks showed that participants using low-medium resistance inhalers did not have a difference in PIFR measurements at baseline versus follow-up (65 L/min on visit 1 and 64 L/min on visit 2; $p=0.69$). Of the 14 participants on a high resistance inhaler, there was no difference in baseline and repeated PIFR measurement (38 L/min on visit 1 and 38 L/min on visit 2; $p=0.46$). A study duration of 24 weeks has been selected to ensure adequate duration to capture normal variability of PIFR as well as need for adequate duration to capture COPD exacerbation events (an important exploratory outcome).

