3.3 Study Duration, Enrollment and Number of Subjects

Study duration and timeline: The duration of study is 24 weeks.

Enrollment: Participants will be recruited from UNC Clinics.

Number of subjects: One hundred twenty patients will be enrolled into this study.

Enrollment to ensure balance of seasonal effects across all arms: Enrollment such that the 24 week study period for each subject includes >2 months during the 'exacerbation season' of October – March (this translates into April and May being the only months to not enroll patients). Screening visits can be undertaken during these two months (April and May).

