4.2 Study Visits

There will be six study visits/encounters over a 22-26 week period as shown in the Study Procedures and Assessments Table. Two study visits will occur at the UNC Clinics (Visits 1 and 2)

and four visits will only involve a telephone interview of subjects by study personnel (Visits 3, 4, 5, and 6).

Visit 1- Screening Visit

At Visit 1, after obtaining written informed consent, a clinical history will be obtained from the patient and if the subject meets all inclusion and exclusion criteria, a CAT score will be determined. The patient will undergo PIFR assessment based on prescribed DPI. PIFR will be recorded with best approximation to nearest 1 L/min. Subjects will be excluded if PIFR > 90 L/min based on Ellipta® and Diskus® setting or inability to achieve minimum PIFR for prescribed DPI setting (< 30 L/min for Handihaler®, < 60 L/min for Ellipta®, Diskus®, or Inhub®). The PIFR will be performed in triplicate by the patient at the recommended device setting (based on patient's DPI specific internal resistance) in the physical position (e.g. sitting) that the patient normally uses to self-administer their inhaler(s). Further, they will be instructed to perform the PIFR consistent based on the manufacturer instructions for proper DPI inhalation technique (e.g. Ellipta®, Diskus® DPI, , Inhub®) "Breathe out gently and breathe in steadily and deep"). For the Handihaler®, subjects will be instructed as follows – "Breathe out completely in one breath. Empty your lungs of air. Breathe in deeply until your lungs are full." If the patient meets the inclusion and exclusion criteria including a PIFR < 90 L/min, they can proceed to Visit 2 (Enrollment) either during the same encounter or scheduled within 30 days. If there is greater than 30 days between Visit 1 and 2, another informed consent will be reviewed and signed.

For inclusion, historical spirometry is required to be documented to ensure patients meet the GOLD definition of COPD using airflow obstruction. Most recent spirometry data will be used for characterization of the enrolled cohort. No spirometry testing will be performed as part of this study.

Visit 2- Enrollment Visit

- A physical examination including measurement of waist circumference (measured in inches horizontally through the narrowest part of the torso, between the lowest rib and the iliac crest)
- Medical history (includes exacerbations history)
- COPD medication use (maintenance and reliever)

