- We will use mixed models to explore associations of monthly PIFR averages over time and clinical and demographic factors. Subjects will be considered as random factor, other variables will be considered fixed effects.
- Association of PIFR with CAT score, mBORG score and mMRC
 - Association of PIFR and CAT scores at V1, V3, V4, V5, V6 (for PIFR, use the measurement in the week of each telephone follow-up, or the month average)

- Correlation of change in CAT scores with change in PIFR from baseline after 24 weeks
- Association of PIFR and mBORG score at V2, V3, V4, V5, V6
- Association of PIFR and mMRC scores at V1, V3, V4, V5, V6 (for PIFR, use the measurement in the week of each telephone follow-up, or the month average)

For COPD exacerbation analyses, the proportion of patients with COPD exacerbations (from Kaplan Meier curve) and the rate of exacerbations occurring during follow-up will be reported along with 95% CI. A patient will be considered censored for exacerbations at the time of the last documented visit, the end of the study, the switching of device (between medium and high resistance DPI) or death (whichever occurs earlier), if they did not experience an exacerbation before. The exacerbations will be reported overall and stratified by severity. The associations between exacerbations and PIFR will be explored in different ways, for all exacerbation, stratified by severity of exacerbations, and stratified by device.

- The rate of exacerbations and sPIFR will be analyzed with negative binomial models (or another model if more appropriate).
- For patients with exacerbations, the mean of PIFR in the week before, of, and after each exacerbation will be calculated and reported.

All tests with p value < 0.05 will be interpreted nominally as statistically significant.

Missing data

- No imputation for PIFR
- No imputation for COPD exacerbations
- No imputation for CAT, mBORG and mMRC

Sample Size and Power

In this application, we propose to recruit 120 COPD participants for study enrollment. There are several rationales for this sample size selection.

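### Section 3.3: closing only April and May does not give every patient more than two months in October–March; February, March and early-June entrants fall short

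*Combined protocol and SAP*

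**What the plan says.** The enrolment paragraph of Section 3.3 has three parts.

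- **Purpose:** "Enrollment to ensure balance of seasonal effects across all arms".
- **Rule:** the "24 week study period for each subject includes >2 months during the" exacerbation season, defined as October to March.
- **Stated consequence:** "this translates into April and May being the only months to not enroll patients". Screening, but not enrolment, may go on in those two months.

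The same section fixes follow-up: "The duration of study is 24 weeks". Appendix 1 times the last telephone visit at 24 weeks after Visit 2, plus or minus 2 weeks, and Section 4.2 says "There will be six study visits/encounters over a 22-26 week period". Section 1.3 justifies the length of follow-up partly by the "need for adequate duration to capture COPD exacerbation events (an important exploratory outcome"). No other section restricts entry in February, March or June.

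**The concern.** The rule and the month list stand in one sentence, and the list is presented as following from the rule. A patient enrolled on 31 March has one day left in the season and finishes before the next season opens, yet March is an open month. Two months of the season cannot be reached from there.

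The list is what recruiting staff can apply directly. If they do, planned in-season follow-up runs from 1 to 168 days, in a design that says it balances season. The outcome most exposed is exacerbations, both occurrence and rate; the sPIFR rate may be affected too. Section 6.3 states that "The rate of exacerbations and sPIFR will be analyzed with negative binomial models" and names no term for season or calendar time, so nothing in the analysis would pick up the difference. The two device cohorts would differ in season only if they accrue in different months, and the documents do not say whether they will.

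**Working it through.** **Inputs**
- Follow-up: 24 weeks = 168 days from Visit 2 (Section 3.3, Appendix 1).
- Season: 1 October to 31 March (Section 3.3).
- Requirement: strictly more than two months in season, for each patient (Section 3.3).
- Tolerance for a sensitivity check: 22 to 26 weeks = 154 to 182 days (Section 4.2, Appendix 1).
- Planned enrolment: 120 (Section 3.3).

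**Formula.** For entry date e, with the entry day as day 1, the last day is e + 167. In-season days D are:
- entry January to March: D = (31 March − e) + 1, as follow-up ends before 1 October;
- entry April to July: D = (e + 167) − 30 September, or 0 if negative.

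**Result by entry month (non-leap year, 168 days)**

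| Entry month | In-season days | Section 3.3 list | More than 2 months? |
|---|---|---|---|
| January | 60–90 | open | yes, in calendar months |
| February | 32–59 | open | no |
| March | 1–31 | open | no |
| April | 0–14 | closed | no |
| May | 15–45 | closed | no |
| June | 46–75 | open | only from 17 June |
| July | 76–106 | open | yes |
| August–December | at least 91 | open | yes |

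**The plan's own figure.** April and May do fail, as the protocol says. That they are the only such months is not reproduced.

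**February and March.** A 1 February entrant has 28 + 31 = 59 days, exactly two calendar months and so not more than two. A 31 March entrant has 1 day; follow-up ends on 14 September at 24 weeks and on 28 September at 26 weeks, both before 1 October. The February and March counts are therefore identical at 154, 168 and 182 days.

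**June.** Entry on 16 June ends on 30 November: 31 + 30 = 61 days, exactly October plus November. Entry on 17 June gives 62 and is the first to qualify.

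**No threshold rescues the list.** Admitting every March entrant needs a threshold of at most 1 day, but then every May entrant (15–45 days) would qualify too. The order is in fact reversed: entrants on 18–31 May are barred with 32–45 days, more than any permitted March entrant.

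**Size.** Permitted entry days: 365 − 30 − 31 = 304.
- 24 weeks: 28 + 31 + 16 = 75; 75/304 = 24.7%.
- 22 weeks: 28 + 31 + 30 = 89; 89/304 = 29.3%.
- 26 weeks: 28 + 31 + 2 = 61; 61/304 = 20.1%.
- February and March alone, at any of these lengths: 59/304 = 19.4%.
- Reading two months as a fixed 59, 60, 61 or 62 days, at 24 weeks: 73, 75, 77 or 79 failing days. With cut-offs of 60 or more, the last one to three days of January also fail.

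With uniform accrual over the permitted days: 120 × 75/304 = 29.6 patients, of whom 120 × 59/304 = 23.3 enter in February or March.

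**The case against.** The strongest points on the other side concern edges, weight and remedy, not the contradiction itself.

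- **The edges are softer than exact dates suggest.** The protocol writes the 48-hour criterion for a mild exacerbation with both a strict and a non-strict inequality, so at least two months may have been meant here. Then 1 February and 16 June qualify, and the failing days go from 75 to 73. Counting the end day as well moves the June edge by a day. This stands, but it changes nothing of substance.
- **June depends on the length of follow-up.** At 26 weeks only 1–2 June fail. This stands, and it is why February and March carry the point.
- **The consequences are limited.** The primary analysis is a descriptive proportion, the device strata serve recruitment only, and the study is not powered to compare inhalers. The documents give no seasonal effect size and no accrual calendar, so the true number affected could be well above or below 30. This stands as a limit on the harm.
- **Covariate adjustment goes beyond correcting the text.** Section 6.3 already allows another model where more appropriate. Entry month as a category would also spend 9 degrees of freedom on about 12 patients per month. That is a fair reason to prefer a single covariate. For a rate, splitting observed person-time by season is a legitimate alternative. What should be avoided is each patient's total of observed in-season days as a covariate, because it depends on censoring: "A patient will be considered censored for exacerbations at the time of the last documented visit", or earlier on a device switch or death.

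**Conclusion.** The point holds. The month list in Section 3.3 does not deliver the property the same sentence claims, under any convention tried: end day counted or not, leap year or not, strict or non-strict inequality, 59 to 62 days. The firm core is February and March, 59 of 304 permitted entry days (19%), which does not depend on follow-up between 22 and 26 weeks; a non-strict or leap-year reading could at most admit 1 February. At exactly 24 weeks the first half of June brings the total to 75 (25%; 73–79 across readings of two months).

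The figure of about 30 of 120 patients assumes that staff follow the month list and that accrual is uniform. If they apply the rule patient by patient, nobody falls short, but then the month list is wrong. The N=120 precision calculation is unaffected. This should be corrected, but it does not threaten the primary analysis.

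**What to change.** Make the rule and the month list in Section 3.3 agree. There are two ways.

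1. **Cheap version.** Keep the April–May closure, withdraw the claim of more than two months, and state that planned in-season follow-up ranges from 1 day (31 March entry) to 168 days. In Section 6.3, add planned in-season days to the exploratory exacerbation and sPIFR rate models: the number of October–March days in the 168 days from Visit 2, fixed at enrolment. Report its distribution by device cohort. The cost is a wording change and one covariate computed from a date already held; the stated design property is given up.
2. **Version that delivers the property.** Close enrolment from 1 February to 16 June. That is 28 + 31 + 30 + 31 + 16 = 136 closed days instead of 61, leaving 229 entry days a year instead of 304, so accrual is slower. Planned in-season days would still range from 60 to 168, so the closure alone does not secure seasonal balance and the covariate remains worth having.

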3.4 Study Population

Our study population will be outpatients with moderate, severe, or very severe COPD.

Participants will be recruited from multiple sources as described above.

Inclusion Criteria:

- Age > 50 years-old
- Spirometry-confirmed diagnosis of COPD (FEV1/FVC <0.70)
- GOLD II-IV based on existing spirometry results
- CAT score > 10
- For high resistance DPI, baseline PIFR < 90 L/min (InCheck DIAL®) and >=30 L/min; for medium resistance DPI, PIFR ≤ 90 L/min (InCheck DIAL®) and >=60 L/min. Handihaler is a high resistance DPI. Examples of medium resistance DPI: Anoro, Incruse, Breo Ellipta®, Advair® Diskus®, or Wixela® Inhub® DPI
- History of smoking tobacco products > 10 pack years
- Prescribed at least one daily maintenance DPI with no change in prescription within the four weeks prior to the Enrollment Visit
- One or more exacerbations of COPD requiring systemic corticosteroids within last 3 years
- Patients will be enrolled with regards to the below pre-specified characteristics based on gender and the prescribed maintenance inhaler(s) as follows (note that patients are commonly prescribed multiple inhalers):
 - Male : Female ratio 1:1 (+ 10%)
 - Target recruitment stratified to two treatment arms:

- N=60 patients receiving medium resistance DPI (Anoro, Incruse, Breo Ellipta®, Advair® Diskus®, or Wixela® Inhub® DPI) with planned recruitment to include 50% of participants on Diskus® and 50% on Ellipta®
- N= 60 patients receiving high resistance DPI (Spiriva Handihaler® DPI)

For all study participants, participants may also receive another MDI, Respimat® inhaler, or DPI (e.g. Breo Ellipta® + Spiriva Respimat®, Symbicort MDI® + Spiriva Handihaler®, Advair Diskus® + Spiriva Handihaler®, Wixela® Inhub® + Spiriva Handihaler®) Subjects will be placed into one of the two cohorts based on the DPI, if on more than one DPI, they will be placed into the cohort for the DPI with the highest resistance (Handihaler>Ellipta=Diskus=Inhub). These strata are for recruitment only, and PIFR measurement for both DPIs will be recorded and used in analyses.

Exclusion Criteria:

- Inability to demonstrate proper technique for the InCheck DIAL® device
- Inability to achieve minimum PIFR for prescribed DPI(s) at screening/enrollment visit (< 30 L/min for e.g., Handihaler® (High resistance DPI), < 60 L/min for Ellipta® (Medium resistance DPI))
- Neuromuscular disease associated with weakness
- Any condition that, in the opinion of the site investigator, would compromise the subject's ability to participate in the study.
- Pneumothorax within the past 4 weeks

4 STUDY PROCEDURES

4.1 Home Monitoring

Subjects will record their PIFR using the InCheck DIAL® and modified Borg dyspnea score three times weekly (MWF) when clinically stable and daily while respiratory symptoms worsen per patient self-assessment. At each session, the participant will repeat efforts three times, with the highest of the three repeated efforts being recorded by the participant. They will be asked to perform the PIFR for the DPI(s) they are receiving at home (Ellipta®, Inhub®, Diskus® or Handihaler®) using the InCheck DIAL®. If on more than one DPI, patient will record PIFR for each device. PIFR will be recorded with best approximation to nearest 1 L/min.

4.2 Study Visits

There will be six study visits/encounters over a 22-26 week period as shown in the Study Procedures and Assessments Table. Two study visits will occur at the UNC Clinics (Visits 1 and 2)

and four visits will only involve a telephone interview of subjects by study personnel (Visits 3, 4, 5, and 6).

Visit 1- Screening Visit

At Visit 1, after obtaining written informed consent, a clinical history will be obtained from the patient and if the subject meets all inclusion and exclusion criteria, a CAT score will be determined. The patient will undergo PIFR assessment based on prescribed DPI. PIFR will be recorded with best approximation to nearest 1 L/min. Subjects will be excluded if PIFR > 90 L/min based on Ellipta® and Diskus® setting or inability to achieve minimum PIFR for prescribed DPI setting (< 30 L/min for Handihaler®, < 60 L/min for Ellipta®, Diskus®, or Inhub®). The PIFR will be performed in triplicate by the patient at the recommended device setting (based on patient's DPI specific internal resistance) in the physical position (e.g. sitting) that the patient normally uses to self-administer their inhaler(s). Further, they will be instructed to perform the PIFR consistent based on the manufacturer instructions for proper DPI inhalation technique (e.g. Ellipta®, Diskus® DPI, , Inhub®) "Breathe out gently and breathe in steadily and deep"). For the Handihaler®, subjects will be instructed as follows – "Breathe out completely in one breath. Empty your lungs of air. Breathe in deeply until your lungs are full." If the patient meets the inclusion and exclusion criteria including a PIFR < 90 L/min, they can proceed to Visit 2 (Enrollment) either during the same encounter or scheduled within 30 days. If there is greater than 30 days between Visit 1 and 2, another informed consent will be reviewed and signed.

For inclusion, historical spirometry is required to be documented to ensure patients meet the GOLD definition of COPD using airflow obstruction. Most recent spirometry data will be used for characterization of the enrolled cohort. No spirometry testing will be performed as part of this study.

Visit 2- Enrollment Visit

- A physical examination including measurement of waist circumference (measured in inches horizontally through the narrowest part of the torso, between the lowest rib and the iliac crest)
- Medical history (includes exacerbations history)
- COPD medication use (maintenance and reliever)
- Patient-reported outcomes (PROs)
 - CAT score (COPD Assessment test)
 - mMRC score (modified Medical Research Council)
 - mBorg score (modified Borg dyspnea score)

- PIFR measurement in three different physical positions – sitting, standing, and lying tilted at 45° with head forward. (repeated using PIFR setting for each DPI patient is receiving)
- Pre- and post-bronchodilator PIFR measurement in sitting position
- Subject instructed on proper use of PIFR device and recording of PIFR measurement and modified Borg dyspnea score using the provided Study Notebook
- Subject instructed to mail PIFR and modified Borg dyspnea score on a monthly basis to the research team using supplied self-addressed, stamped envelopes

Visits 3, 4, 5, and 6 - Telephone Visits

At Visits 3, 4, 5, and 6 (at 4, 8, 12 , and 24 weeks after Visit 2 -permissible ± 2 week window for each visit), study personnel will contact the participant by telephone to obtain PIFR and symptom questionnaires recordings during the preceding 2 weeks. A time period less than 2 weeks is acceptable if the subject had mailed in their monthly log recently. PIFR measurements and respiratory symptom questionnaires (modified Borg dyspnea score only) will have been recorded by study participants using a Study Notebook. PIFR will be recorded for each DPI the patient is receiving. A CAT score, mBorg, and mMRC will also be determined by study personnel as part of each visit. Ascertainment of exacerbations, medication adherence, and change in inhaler regimens will be completed. In part, the telephone visit will be undertaken to increase subject's compliance to study procedures.

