Patient-related impediments to achieving this minimum inspiratory flow in the COPD population include age, gender, and stature (Seheult, [Mahler 2013](#)). Mahler reported that persons most likely to have an impaired PIFR are the elderly and females, (Mahler 2013), thus the rationale for having an equivalent number of males and females participate in the present study. Another factor that could affect inspiratory flow in the COPD patient is the physical position of the patient when using their DPI (standing, sitting, supine). It has been shown that peak expiratory flow rate (Wade) and other pulmonary function test measures (Wallace) including forced residual capacity are lower in a supine position than in a standing position. Therefore it is possible that a hospitalized COPD patient in a supine position, particularly with worsened respiratory status, could have decreased lung deposition from a DPI because of impaired inspiratory ability. Another scenario that a COPD patient could have impaired inspiratory capability is a morbidly obese subject using their DPI in a sitting position, where the diaphragm is displaced upwards and thus the lungs are less capable to generate a strong inspiratory effort. To our knowledge, the effect of physical position of the COPD patient on PIFR has not been investigated.

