4.5 Rescue medication administration (if applicable)

Inhaled albuterol 2 puffs by metered dose inhaler will be administered as part of pre- and post-PIFR measurement at Visit 2

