5.1.4. PIFR Measurements

Study visits PIFR: PIFR measurements will be collected using the In-Check G16 DIAL® which is a simple, hand-held low range inspiratory flow device that measures PIFR via a brief inspiratory maneuver (APPENDIX 5). The device includes a one-way disposable mouthpiece, measurement diaphragm, and a directly visualized PIFR scale. The device also includes an adaptor with adjustable resistance to mimic nine resistance groups encompassing the popular MDIs and DPIs currently available. After each inspiratory maneuver to a set resistance, the PIFR score will be visualized on the scale and recorded. Subjects will perform the PIFR in the following manner:

Patients receiving Handihaler® and/or Ellipta® and/or Diskus® and/or Inhub®

- For testing during study visits, perform PIFR in the physical position they most commonly use when self-administering their maintenance inhaler(s)
- Perform PIFR using the inspiratory effort described by the manufacturer (Ellipta®, Diskus®, and Inhub®)- breathe out fully, then take a long, steady deep breath; ‘breathe out all the way, then breathe in slowly and deeply’ For the Handihaler®, subjects will be instructed as follows – “Empty your lungs of air. Breathe in deeply until your lungs are full.”
- Measurements will be collected on each prescribed DPI resistance setting. PIFR will be recorded with best approximation to nearest 1 L/min. Ample time will be given to any patients who may be feeling short of breath or fatigued.

Home measurement of PIFR: Using the In-Check G16 DIAL®

- Perform PIFR in physical position most commonly used when self-administering maintenance inhaler(s)
- Perform PIFR (proper setting) for each maintenance DPI patient is receiving
- Use maximum inspiratory effort, by first breathing out fully, and breathing in as hard and fast as possible, and as above, repeat the maneuver two more times, recording the highest value.

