16 APPENDIX 1. STUDY PROCEDURES AND ASSESSMENTS

Visit number	V1 ^a	V2	V 3,4,5,6
Procedures and assessments	Screening Visit	Enrollment Visit	Telephone Follow-up Visits
Target time(s) and allowable time frames		At same time as or within 1 month of Screening Visit	At 4, 8, 12, 24 weeks after V2 (± 2 weeks)
Informed consent	X		
Clinical history	X	X	
Prior medication history	X	X	
Inclusion and exclusion criteria	X	X	
Physical examination including waist circumference		X	
Vital signs measurement		X	
Peak Inspiratory Flow Rate (Performed in triplicate at resistance of all DPIs the patient is receiving)	X	Pre- and post-bronchodilator (albuterol) Perform PIFR in three positions (sitting, standing, and lying at 45° angle with head tilted forward) [#]	Done 3x/wk. (each session in triplicate with highest value recorded) at home by patient after enrollment [#] (Daily during worsened symptoms)
COPD Assessment Test score (CAT) questionnaire	X	X	X
Modified Borg Dyspnea Score (mBorg)		X	X Done 3x/wk at home by patient after enrollment
Modified Medical Research Council questionnaire (mMRC)		X	X
COPD exacerbation history*	X	X	X
COPD medication use and adherence	X	X	X

^aMild, moderate and severe exacerbations will be defined as:

Mild – doubling use of inhaled rescue medication ≥ 48 hours and not meeting definition of moderate or severe; Moderate – increased rescue medication and oral corticosteroid, not requiring hospitalization; Severe – hospitalization for exacerbation

[figure not shown]
PIFR will be performed before performing spirometry (if spirometry is performed at that visits) using InCheck Dial settings for each DPI patient is receiving

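### Visit 2 sets neither the order of the three body-position PIFR measurements nor their timing relative to albuterol, so the exploratory position comparison may be inseparable from order or bronchodilator effects

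*Combined protocol and SAP*

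**What the plan says.** Section 4.2 lists, for Visit 2, "PIFR measurement in three different physical positions" (sitting, standing and reclining at 45°), to be repeated for each DPI the patient uses. The next item is "Pre- and post-bronchodilator PIFR measurement in sitting position". Appendix 1 puts both in one cell in the reverse order: "Pre- and post-bronchodilator (albuterol) Perform PIFR in three positions". Section 4.5 adds only that "Inhaled albuterol 2 puffs by metered dose inhaler will be administered as part of pre- and post-PIFR measurement at Visit 2".

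The Appendix 1 row heading specifies efforts "Performed in triplicate at resistance of all DPIs the patient is receiving". Section 5.1.4 provides for rest, without an interval: "Ample time will be given to any patients who may be feeling short of breath or fatigued".

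Body position is a named predictor in the exploratory objectives (section 2.1). Section 1.3 presents it as a knowledge gap, stating that to the authors' knowledge "the effect of physical position of the COPD patient on PIFR has not been investigated". The analysis in section 6.3 is a descriptive summary of PIFR by position, with no term for order or for bronchodilator status.

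**The concern.** A within-patient comparison of three conditions measured one after another is open to order effects. Repeated maximal inspirations may tire patients with GOLD II-IV disease and lower the later values. Practice may raise them. If everyone is tested in the same order, position and order coincide exactly, and no later analysis can tell them apart. If the order varies but is not recorded, it cannot be adjusted for.

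Albuterol is given at the same visit. If some position readings are taken before it and others after, its effect on PIFR enters the position contrast directly.

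What is at stake is the reading of a result the protocol presents as new. A low reclining value could reflect being tested last, and a high one could reflect practice or albuterol. The order and timing actually used cannot be recovered after Visit 2 if they were not written down.

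**Working it through.** **The plan's own figure.** The only sample-size basis is the precision table in section 6.3. For a proportion of 40% and a half-width of 8.8%: N = 1.96² × 0.40 × 0.60 / 0.088² = 119.05, rounded up to 120. The table reproduces. It concerns the primary endpoint and says nothing about position contrasts.

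**Effort count at Visit 2** (three efforts per position per DPI setting):
- Positions only: 3 × 3 = 9 for one DPI, 18 for two.
- If the sitting value also serves as the pre-bronchodilator value, one more set of three is needed after albuterol: 12 for one DPI, 24 for two.
- If a separate sitting pair is taken: 15 for one DPI, 30 for two.
- Section 4.2 allows Visits 1 and 2 in the same encounter, which adds 3 per DPI.

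**Where albuterol can fall:**

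| Sequence | Effect on position contrasts |
|---|---|
| All three positions before albuterol | None |
| All three positions after albuterol | No pre/post mix; the contrast describes the bronchodilated state |
| Series straddles albuterol, or a pre-albuterol sitting value is compared with post-albuterol standing and reclining values | The full albuterol effect enters the contrast |

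The documents exclude none of the three rows.

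**Illustration of order bias.** The inputs are assumptions, not document figures: within-patient SD (SDw) of 5, 7.5 or 10 L/min, and a linear drift d per position slot. The lowest SD borrows the 5 L/min device repeatability in section 1.3.
- Standard error of a paired position difference: SE = SDw × √2 / √120 = 0.645, 0.968 or 1.291.
- 95% half-width: 1.96 × SE = 1.27, 1.90 or 2.53 L/min.
- Bias of first versus third slot in a fixed order: b = 2d. For d = 0.5, b = 1 L/min; for d = 1, b = 2 L/min.
- Chance of nominal significance (two-sided 0.05) with no true position effect: 1 − [Φ(1.96 − b/SE) − Φ(−1.96 − b/SE)].

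| SDw (L/min) | d = 0.5 | d = 1 |
|---|---|---|
| 5 | 34% | 87% |
| 7.5 | 18% | 54% |
| 10 | 12% | 34% |

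Section 6.3 describes PIFR per device. With 60 patients at one setting, the half-width is 1.96 × SDw × √2 / √60, or 1.79 L/min at SDw = 5 and 3.58 L/min at SDw = 10. The bias is unchanged.

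**Effect of rotation.** Three positions have six orders. At N=120 that is 120/6 = 20 patients per order. Each position then stands in each slot in two of the six orders (40 patients), so its mean slot is the same as the others' and a linear drift adds zero bias to every position contrast.

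**The case against.** The strongest reply is that the lists in section 4.2 and Appendix 1 are not sequences. Section 4.2 lists device instruction after the PIFR measurements and the questionnaires before them, while Appendix 1 lists PIFR before the questionnaires. This stands: neither list prescribes an order. It also means that the order is undefined.

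A reader might infer that every patient is tested sitting, then standing, then reclining. The documents do not support that. Sections 1.3 and 6.3 name standing first, so a common fixed order is possible but not established.

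A reader might also infer from the reversed listing that albuterol contaminates the contrast. That does not follow. Taken literally, section 4.2 puts all positions before albuterol and Appendix 1 puts all of them after it. Contamination needs a straddled series or a reused sitting value.

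Nor can one say that the bias would match or exceed the confidence interval. The drift is unknown in size and sign, since fatigue and learning pull in opposite directions. At 0.5 L/min per slot the bias of 1 L/min is below the smallest half-width above (1.27). For patients on two DPIs, the gap between first and third position at one setting is 12 efforts only if both settings are tested at each position; if the series is run separately for each DPI, it is 6.

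The safeguards count too. The highest of three efforts is used, patients practise at Visit 1, those who cannot show proper technique are excluded, and tired patients may rest. These reduce order effects. They do not remove a systematic one, because the rest is unquantified and the order is not recorded.

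Finally, position is exploratory and its analysis descriptive, with no position test specified. That limits the weight of the point.

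**Conclusion.** The point holds as a gap in the design of an exploratory comparison. The plan allows a single order for all patients and allows the series to straddle albuterol. In either case the position differences could not be interpreted as effects of position alone. Confounding is possible under the plan, not certain.

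The size is unknown from the documents. Under the assumed SDs of 5 to 10 L/min and N=120, half-widths are about 1.3 to 2.5 L/min. An assumed drift of 1 L/min per slot in a fixed order gives a bias of 2 L/min, enough to matter at the lower SDs and less so at the higher. The primary endpoint does not use these readings: home PIFR is taken in the patient's usual position. N=120 stands. This is a cheap improvement, not a threat to the study's main result.

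**What to change.** - Reconcile section 4.2 and Appendix 1 so that all three positions are measured on one side of albuterol. From the measurement standpoint, completing them before it is the simpler arrangement: the sitting value then serves as the pre-bronchodilator value and the count is 12 efforts per DPI, not up to 15.
- Assign the six position orders in rotation by study ID, pre-printed on the Visit 2 form (20 patients per order at N=120). Section 4.7 also gives IDs to screen failures, so the counts will be approximate unless the rotation follows actual enrolment.
- State a rest interval between positions, and record the order used and the time of each set and of albuterol.
- In section 6.3, report position contrasts within patient and per device setting, with a period term (first, second, third). This fits the mixed models with subject as random factor already planned there.

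The cost is a revised form and slightly more coordinator attention. No extra measurements or patients are needed.
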